## **INTRODUCTION**

Differentiating gastroesophageal reflux (physiological, GER) from GER disease (pathological, GERD) remains a challenge in ICU infants (1-5). Troublesome symptoms (6) often trigger a battery of empiric therapies, such as acid-suppression, feeding modifications, and positional changes (7-10). Prevalence of GERD ranges from 2–30% across neonatal intensive care unit(NICU)s in the United States, along with a 13-fold variation in therapies, imposing an additional economic burden of over \$70K per admission and 30 hospital days (9-13).

The infant GER questionnaire-revised (I-GERQ-R) is a survey of parental/provider perception of symptom burden thought to be due to GERD, with a 6 point decrease indicating clinical improvement (14). Although, prior clinical trials for GERD pharmacotherapy have used symptom-based criteria (15-18), few have evaluated the effectiveness of a bundled holistic approach, i.e., a combination of pharmacologic-, feeding-, and positional approaches in NICU patients. Improvement of parental perception of symptoms and total GER events with left lateral position and proton pump inhibitor (PPI) (8), reduction of GER events with infants in prone or left lateral post-prandially (19), and conservative strategies for 2 weeks showed improvement with I-GERQ-R scores among one to ten months age (20). We observed that decreased feeding volume and prolonged feeding duration were associated with reduced GER events (21). However, a bundled approach combining targeted acid suppression (limited duration), feeding modifications (volume, position, duration) and postprandial positions has not been rigorously examined in infants with proven esophageal acid reflux index (ARI) severity.

Based on this *rationale*, we have undertaken this clinical trial to determine the effective therapeutic strategies on the clinically meaningful primary outcomes in infants presenting with GERD symptoms who have qualifying ARI criteria. The *objective* of this RCT was to examine the

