## **PATIENTS AND METHODS**

### **STUDY DESIGN AND EXPERIMENTAL PROTOCOL**

This is a single center, single blinded RCT (Clinicaltrials.gov: [NCT02486263](#)) comparing the effectiveness of two feeding strategies combined with the use of a PPI (omeprazole) to manage acid-GERD [GERD Management and Therapy trial (GMT trial)]. This study was approved by the Institutional Research Board (IRB) at Nationwide Children's Hospital, Columbus, OH (IRB # 11-00734). Omeprazole is commonly used off-label in this population within the standard of care (9). Data safety monitoring plan was implemented and monitored quarterly by the Data Safety Monitoring Board (DSMB). Written, signed, and informed parental consent was obtained. Health Insurance Portability & Accountability was followed. Study PI and RN coordinator were available 24/7.

Twenty-four-hour pH-impedance studies were performed (6, 22, 23) (Laborie Medical Technologies, Mississauga, ON, Canada). ARI (duration of esophageal acid exposure, %) was calculated (24). I-GERQ-R symptom score (14, 17, 25) was collected. Demographic and clinical outcomes were managed using research electronic data capture tools (REDCap) tools (26) for up to 2 years from subject enrollment.

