### **PARTICIPANT SELECTION, RANDOMIZATION AND ALLOCATION**

Inclusion criteria were: a) infants admitted with clinical symptoms of GERD between 34-60 weeks postmenstrual age, with physician's intent to treat with acid-suppressive therapy, b) an intake volume of full enteral feeds  $\geq 150$  mL/kg/day, c) room air or supplemental oxygen  $\leq 1$  liter per minute, and d) ARI  $\geq 3\%$  (6, 22-24). Exclusion criteria were: a) infants with known genetic, metabolic or syndromic diseases; b) neurological diseases including  $\geq$  grade III intraventricular hemorrhage or perinatal asphyxia, c) GI malformations or surgical GI conditions, and d) infants on acid suppressive medication at initial evaluation. Randomization was performed among consented subjects who were stratified 1:1 ratio by ARI severity (3%-7%: indeterminate acid reflux and  $>7\%$ : severe acid reflux) and by birth gestation (preterm, full term) into study feeding approach or conventional approach. Permuted Block Randomization with block sizes of 2, 4, 6, and 8 was undertaken by the study statistician (OSU Center for Biostatistics) using a computer-generated allocation and implemented in REDCap. Nurse coordinator enrolled subjects by verifying eligibility, obtaining parental consent, and entering demographic data into REDCap. PI and study staff who evaluated subject clinical outcomes were blinded to study allocation.

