## **STUDY INTERVENTIONS**

### **Interventions**

Providers employ uniform feeding and nutritional practices in our NICU infants as per our standardized guidelines, which applies to nutrient and volume modifications. However, upon randomization and allocation, individual protocols are complied with. Upon completion of screening, enrollment and randomization, the assigned feeding management strategy was relayed to parents and the medical team. Subjects in both arms received omeprazole off label, as a therapeutic choice (27, 28) at a recommended dose of 0.75 mg/kg/dose BID (15, 27, 29). The conventional approach was to not adjust provider recommended feeding strategies (i.e. fed in any

position, duration, volume, and postprandial position). The study approach utilized a modified feeding strategy including: a) feeding in the right lateral position to facilitate intra-prandial gastric emptying (30), b) feeding duration of at least 30 min utilizing pacing when orally fed to ensure completion of prescribed volumes or via pump to ensure steady delivery of milk if gavage-fed (21), c) supine postprandial position (31), and d) limiting total feeding volume to  $\leq 140$  ml/kg/day (21).

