is justifiable in future trials, as nearly 40% of infants are in this severe range, and it is possible to study such a group in larger clinical trials based on pH and impedance criteria, while employing placebo for equipoise. Since time-limited PPI therapy concurrent with feeding strategies was neither shown to be beneficial or associated with adverse effects, we believe that, it is safe to include a completely untreated placebo group in future trials that enroll patients with objectively determined acid-GERD. 2) The management strategies were tightly regulated, as were feeding and testing guidelines, and the treatment was uniformly delivered across the two groups. The patient population was homogeneous and constituted a fair representation from the convalescing NICU population. In addition, the randomized controlled allocation accounted for premature or full-term birth, and the indeterminate or determinate acid-GERD per ARI. Furthermore, the prevalence of oxygen requirement or tube feeding at discharge was not different between groups. 3) Our study trial has many elements of objectivity. Determination of I-GERQ-R and ARI, as well as monitoring feeding methods during the trial are strengths. Thirty-six percent of those with aerodigestive and or cardiorespiratory symptoms perceived by their clinicians to be due to GERD prior to trial consent, were not randomized and were also never treated with a PPI as the esophageal acid exposure was normal (ARI < 3%). In a purely symptom-based clinical trial, all those 688 infants screened would have likely been treated for presumed GERD. In the current study, only those that had true ARI exposure have been randomized and treated. Therefore, the symptom-based approach alone is not the solution to diagnose and treat GERD. Interestingly, perception of symptoms (IGERQR scores) decreased across time regardless of treatment group allocations (**Fig 2**). These findings strongly support maturational effect. As both groups were treated with PPI, placebo-included RCTs are needed to determine if maturation alone will improve objectively determined acid- and non-acid-GERD. 4) Absence of pH-impedance testing to confirm true acid-GERD prior

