**FIGURE 1.**

**Figure 1. Study Enrollment and Randomization.** Depicted is the CONSORT diagram describing participant flow and randomization into the conventional or study bundles, and subjects analyzed for outcomes.

## FIGURE 2

**Figure 2. I-GERQ-R Outcomes.** Depicted is a combination plot by group (boxplots) and individual I-GERQ-R scores (black line represents median). Note that parent perception scores (I-GERQ-R) significantly decreased in both groups at Time-2.

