## 2.0 Objectives

### 2.1 Purpose, specific aims or objectives

- Clinical trial based on objective evaluation of symptoms scored by blinded independent rater during pH-Impedance studies (Aim 1).
- Investigates the neuro-physiological aspects of the reflexes involved with GERD and its complications (Aim 2).
- Unique to this proposal, we will apply physiologically rational, and safe, therapeutic strategies that have the real potential to ameliorate GERD symptoms/complications. If the proposed aims are achieved, we anticipate:
  - Finding that not only acid, but also feeding volume, position and maturational changes in adaptation underlie the pathogenesis of GERD, and in this way clearly identifying relevant new therapeutic targets for this disease.
  - Understanding the various stimulus-targets and provoked reflexes that lead to sensitization of afferents, and thereby symptoms associated with GERD.
  - Understanding the mechanism(s) underlying functional esophageal disorders in infants, thereby clarifying the pathophysiology of symptoms presumed to be GERD related.
  - Development of cost effective, efficacious methods for the diagnosis and management of GERD in infants.
  - Establishing objective criteria for evaluating the need for anti-reflux surgical procedures in infants.

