## **6.0 Procedures Involved\***

### **6.1 Study design:**

- Study design and setting: This is a Single Center Prospective Randomized, Blinded Controlled Trial. Consented subjects will undergo 1:1 randomization into either innovative feeding strategy and standard therapy arms.
- Patient Population: Potential study subjects are those that are referred by their attending physician for evaluation and management of potential GERD, the key symptoms being irritability and arching, gagging, choking, coughing, aspiration, life threatening events, swallowing problems, and/or failure to thrive. I-GERQ-R questionnaire will be completed as per guidelines. Each patient must have a signed consent from parent/legal guardian prior to initiation of screening for the trial.
- Inclusion Criteria: Hospitalized convalescing infants with aerodigestive symptoms or admitted for GERD symptoms, < 42 weeks GA. Infants will be included if PMA at time of study is  $\geq$  34 wks age and  $\leq$  60 wks. Subjects must be on full enteral feeds defined as  $\geq$  150mL/k/day. Infants must be breathing unaided, and nasal cannula oxygen up to 1 LPM is allowed. In subjects receiving empiric prokinetics or acid suppressive agents, the medications need to be stopped for  $\geq$  72 hr prior to evaluation.
- Exclusion Criteria: Infants with known genetic, metabolic or syndromic disease, neurological diseases such as Grade III or IV intra ventricular hemorrhage or perinatal asphyxia, GI malformations and surgical GI conditions.
- Tests and procedures
  - Twenty-four-hour pH and impedance ordered diagnostically for suspected GERD
  - If RI  $>3$  and infant meets all above criteria, infant randomized into conventional or study group
  - Esophageal manometry performed
  - 4 weeks of the study intervention for the study group and standard treatment for the conventional group while collecting data on symptoms, feeding position, duration and volume

- Omeprazole stopped after 4-week course.
- Repeat esophageal manometry and pH impedance testing done after 1 week off omeprazole (at week 5). If the providers/parents are resistant or refuse to stop the medication, repeat testing will still be done, and the alteration will be noted.

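### The I-GERQ-R half of the primary endpoint is rated by people who knew the allocation, so the stated blinding does not protect it, and the blinded symptom rating named for Aim 1 is neither in the primary endpoint nor reported

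*Combined protocol and SAP*

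**What the plan says.** On blinding, the trial report opens its design section with "This is a single center, single blinded RCT". Its section on participant selection, randomization and allocation adds that "PI and study staff who evaluated subject clinical outcomes were blinded to study allocation". Protocol section 6.1 states "This is a Single Center Prospective Randomized, Blinded Controlled Trial", and section 3.3 (under intention to treat) also uses the word blinded. Neither protocol section says who is blinded.

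On who knew the arm, the Interventions section of the report says that "the assigned feeding management strategy was relayed to parents and the medical team".

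On who produces the score, the Introduction says that the I-GERQ-R "is a survey of parental/provider perception of symptom burden thought to be due to GERD". The Figure 2 legend reads "Note that parent perception scores (I-GERQ-R) significantly decreased in both groups at Time-2". The Discussion, in its third listed strength, says "Our study trial has many elements of objectivity. Determination of I-GERQ-R and ARI".

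On the endpoint, Outcome Measures and protocol section 4.0 define success by full oral feeds and/or a fall of at least 6 points in I-GERQ-R for infants not yet fully orally fed. Infants already on full oral feeds must keep them and also have the 6-point fall.

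On a blinded symptom measure, protocol section 2.1 describes the trial as "Clinical trial based on objective evaluation of symptoms scored by blinded independent rater during pH-Impedance studies (Aim 1". Section 4.0 lists 24-hour pH-impedance at inception and week 5 as a secondary outcome.

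**The concern.** A questionnaire is blinded only if the person who answers it is blinded. Blinding the staff who compile or classify the answers does not change what the parent or provider wrote. Here the respondents had been told the arm, and in the study arm the bundle (position, pacing, volume limit) is visible at every feed. Expectations about it, hopeful or sceptical, could move a perception score across a 6-point threshold.

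A reader who sees a single-blind trial with blinded outcome evaluation, and the I-GERQ-R listed among the objective elements, will take the symptom result as protected from this. The Conclusion then makes firm statements: that feeding modification has no role in decreasing reflux-type symptoms, and that falling scores strongly support maturation. The measure that could check these statements against blinded observation is planned but not shown.

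**Working it through.** **1. Each primary component set against who knew the arm.**

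- I-GERQ-R: answered by parents or providers (Introduction, Figure 2 legend), who were told the allocation (Interventions). Unblinded at source, from the text itself.
- Full oral feeds: section 4.0 defines this by there being no need for tube feeding, with no volume criterion and no blinded adjudicator. Section 6.1 takes data from the medical record, diaries and parent interviews, and from parents after discharge. The people who manage and record feeding were told the arm, but no section names who makes the decision. Exposure is probable, by inference.

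**2. The plan's and report's own figures.**

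- Power: 50 per arm, 40% against 67% (27 taken as percentage points), one-sided 0.025, single look. Power = Φ[(Δ − 1.96·SE0)/SE1]. SE0 = √(2 × 0.535 × 0.465/50) = 0.0998; SE1 = √((0.24 + 0.2211)/50) = 0.0960. This gives Φ[(0.27 − 0.1955)/0.0960] = 78.1%. With SE1 in both places, Φ(2.81 − 1.96) ≈ 80%, the stated figure.
- Primary result: 16/36 against 13/40, uncorrected chi-square 1.15, p = 0.284. The report gives 0.28.

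**3. How much success depends on the score (Table 3).** The tube-fed rows are displaced by one line in the extracted text. Realigned, they pass three checks:

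- Inclusion–exclusion: conventional 11 + 7 − 4 = 14; study 7 + 8 − 2 = 13.
- 6-point falls: conventional 7 + 4 = 11; study 8 + 5 = 13, as in Table 2.
- Oral feeding at Time 2: conventional 11 + 16 = 27; study 7 + 17 = 24, as in Table 2.

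| | Conventional | Study |
|---|---|---|
| Tube-fed, success | 14 | 13 |
| of these, reached full oral feeds | 11 | 7 |
| Tube-fed, success on I-GERQ-R only | 14 − 11 = 3 | 13 − 7 = 6 |
| Orally fed, success (score fall required) | 4 | 5 |
| Successes that need the score | 3 + 4 = 7 | 6 + 5 = 11 |
| All successes | 14 + 4 = 18 | 13 + 5 = 18 |

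The shares are 7/18 = 39% and 11/18 = 61%. Table 2 reports 16 and 13 successes, so these are not shares of the reported primary result. In Table 1, 37 of 76 infants were orally fed at inception, and for them the score is always required.

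The score also moves the contrast. Among tube-fed infants, oral feeding alone is 7/20 = 35% (study) against 11/18 = 61% (conventional), a gap of 26 points. With the score added it is 13/20 = 65% against 14/18 = 78%, a gap of 13 points.

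**4. What a bias of assumed size would do.** The documents give no size, so 5, 10 and 15 points are assumptions. The pooled formula and design of step 2 apply.

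| Assumed shift in study-arm success | No true effect: one-sided error if shift favours bundle | True 27-point effect: power if shift is against bundle |
|---|---|---|
| none | 2.5% | 78% |
| 5 points | 7% | 60% |
| 10 points | 17% | 40% |
| 15 points | 32% | 22% |

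This shows sensitivity only. It is not an estimate of what happened.

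**5. The blinded rating.** Section 2.1 ties it to Aim 1. Neither primary definition includes it and no table reports it. Protocol section 1.0 (secondary objective), section 3.3 (Aim II and the closing paragraph) and section 4.0 keep pH-impedance and symptom indices in the plan.

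**The case against.** The report never says that parents or treating providers were blinded. It limits blinding to the PI and outcome-evaluating staff and openly says who was told. That is fair: the fault lies in leaving unstated what this means for a parent-rated endpoint, and in calling that endpoint objective. The same Discussion item itself later calls the score a perception of symptoms.

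Four stronger readings are tempting, and the documents do not support them.

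- That both primary components are shown to be unblinded. No section names who decides that tube feeds are no longer needed, and Interventions refers to standardized unit guidelines, though it then defers to the assigned protocol. For oral feeding the point remains an inference.
- That only data handling was blinded. The report says that staff evaluating clinical outcomes were blinded, and nothing reduces this to data handling. How blinding was kept is not described: section 17.0 has lab staff reviewing bedside records and telephoning parents weekly. That does not prove unblinding.
- That the blinded measure was dropped. It remains among planned secondary analyses. The Discussion defers mechanistic and symptom-causation outcomes to future reports, and its limitations leave the comparison of I-GERQ-R with true symptoms to further studies.
- That the 39% and 61% shares show bias, or that unblinding explains the null result. The shares show reliance. The 6-point response hardly differs by arm (11/31 = 35% conventional, 13/34 = 38% study, p = 0.82), and the primary result favours the conventional arm (44% against 33%). Bias in favour of the bundle would not produce that. Bias against it cannot be excluded, but no evidence for it is given.

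**Conclusion.** The concern stands for the I-GERQ-R on the documents' own wording: this component of the primary endpoint is unblinded at source, and the blinding statements and the objectivity claim mislead unless qualified. For full oral feeds, exposure is probable but rests on inference.

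The component matters. By Table 3, 18 of 36 successes overall (7 + 11) would not count without it. This assumes the realigned rows, and the conflict with Table 2 (29 successes: 16 + 13) is unresolved. Neither the size nor the direction of any bias can be found from the documents, so the point does not overturn the reported comparison. It limits what can be concluded about symptoms while the blinded rating attached to Aim 1 is absent from both the primary endpoint and the report.

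**What to change.** 1. In the report's design and allocation sections and in protocol sections 3.3 and 6.1, state that the PI and outcome-evaluating staff were blinded, and that parents and the medical team, who rate the I-GERQ-R and manage feeding, were not. Remove the I-GERQ-R from the objective elements in the Discussion.
2. Reconcile section 2.1 with section 4.0. Name the blinded-rater symptom scores and indices from the two pH-impedance studies as the supportive symptom outcome for Aim 1, and report them by arm beside the I-GERQ-R responder rate. Say how the rater was kept unaware of the arm at Time 2. Limit the symptom statements in the Conclusion until this is shown.
3. Reconcile the success counts in Tables 2 and 3.
4. If recorded, report who answered the I-GERQ-R at each time. A rule requiring the same respondent cannot be imposed after the May 2019 data lock, and nothing shows that respondents changed.

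The cost is revised wording, one table reconciliation and one analysis of data the protocol already plans to collect. The design will be described less favourably. Time-2 pH-impedance is likely to be missing in some infants. Revision 3 and section 6.1 allow Time-2 testing without stopping omeprazole, so drug status at the test must be reported with the result.

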## **STUDY INTERVENTIONS**

### **Interventions**

Providers employ uniform feeding and nutritional practices in our NICU infants as per our standardized guidelines, which applies to nutrient and volume modifications. However, upon randomization and allocation, individual protocols are complied with. Upon completion of screening, enrollment and randomization, the assigned feeding management strategy was relayed to parents and the medical team. Subjects in both arms received omeprazole off label, as a therapeutic choice (27, 28) at a recommended dose of 0.75 mg/kg/dose BID (15, 27, 29). The conventional approach was to not adjust provider recommended feeding strategies (i.e. fed in any

position, duration, volume, and postprandial position). The study approach utilized a modified feeding strategy including: a) feeding in the right lateral position to facilitate intra-prandial gastric emptying (30), b) feeding duration of at least 30 min utilizing pacing when orally fed to ensure completion of prescribed volumes or via pump to ensure steady delivery of milk if gavage-fed (21), c) supine postprandial position (31), and d) limiting total feeding volume to  $\leq 140$  ml/kg/day (21).

## OUTCOME MEASURES

The *a priori primary end-point* was achieving independent oral feeds and/or a six-point decrease in I-GERQ-R score at 5 weeks or sooner, whichever was earliest at discharge. *To clarify further, there were 2 scenarios:* 1) Among infants who were transitioning to oral feeds (gavage fed) at inception: success was defined as achieving full oral feeds or a  $\geq 6$ -point decrease from baseline I-GERQ-R. 2) Among infants who were on full oral feeds at inception, success was determined if full oral feeds were maintained plus a  $\geq 6$ -points decrease from baseline I-GERQ-R. *Secondary end-points* included growth metrics (weight, length and head circumference), supplemental oxygen, economic metrics (LOHS), long-term feeding outcomes at 6 months and 1 year, and developmental outcomes at 2 years (32, 33).

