**Table 2. Primary and Secondary Clinical Outcomes and Compliance Measures**

Primary Outcome (intent-to-treat analysis)	Overall (N = 76)	Conventional (N = 36)	Study (N = 40)	P-value
A priori clinical outcome Success, n (%)	29 (38)	16 (44)	13 (33)	0.28
Secondary Outcomes	Overall (N = 72)	Conventional (N = 35)	Study (N = 37)	P-value
I-GERQ-R decrease by 6 – n (%)	24/65 (37)	11/31 (35)	13/34 (38)	0.82
Feeding Outcome at Time 2 – n (%)				0.26
PO	51 (71)	27 (77)	24 (65)	
Transition (PO + Tube)	18 (25)	8 (23)	10 (27)	
Tube	3 (4)	0 (0)	3 (8)	
Length of hospital stay – days	108 [82 - 128]	108 [83 - 125]	98 [81 - 132]	0.89
Hospital stay Inception to Discharge – days	25 [11 - 45]	23 [3 - 39]	27 [16 - 47]	0.26
Weight Growth Velocity (GV) – g/day	27.1 (9.4)	26.5 (7.2)	27.6 (11.1)	0.64
Length GV – cm/day*	0.1 (0.1)	0.1 (0.1)	0.1 (0.1)	0.88
Head Circumference GV – cm/day*	0.1 [0.0 - 0.1]	0.1 [0.0 - 0.1]	0.1 [0.0 - 0.1]	0.87
Feeding Method at Discharge – n (%)				0.32
PO	54 (75)	29 (83)	25 (68)	
Transition (PO + Tube)	14 (19)	5 (14)	9 (24)	
Tube	4 (6)	1 (3)	3 (8)	
Oxygen Requirement at discharge – n (%)	16 (22)	9 (26)	7 (19)	0.49
Compliance to Feeding Methods				
Total Fluid Volume (TFV)				
TFV at Inception- #	N/A	150 [147, 152]	150 [149, 156]	0.8
TFV at Time 2- #	N/A	143 [134, 148]*	133 [126, 137]*	<0.001
# days TFV ≤ 140 / kg / day	N/A	10 [2, 26]	22 [11, 31]	0.005
TFV compliance (TFV <140/kg/d for >75% of time)	N/A	9 (26)	27 (73)	<0.001
Position				
Feeding Position, RSL, %	N/A	5 [1, 17]	78 [12, 94]	<0.001
Feeding in RSL >75% of the time, %	N/A	0 (0)	21 (57)	<0.001
Supine Position Post-Prandial, %	N/A	50 [40, 66]	87 [74, 96]	<0.001
Supine Position Post-prandial >75% of the time, %	N/A	7/34 (21)	27/36 (75)	<0.001
Feeding Duration				
% time feed duration >30 min, %	N/A	4 [0, 37]	15 [0, 69]	0.15
Feeding Duration at Inception, min	N/A	23 [17, 41]	30 [19, 34]	0.64
Feeding Duration at Time 2, min	N/A	23 [18, 28]	26 [20, 30]	0.15
Long-term Follow-up†				
Feeding Method at 6 months – n (%)				0.65
PO	36/50 (72)	21/27 (78)	15/23 (65)	
Transition (PO + Tube)	10/50 (20)	4/27 (15)	6/23 (26)	
Tube	4/50 (8)	2/27 (7)	2/23 (9)	
Feeding Method at 1 year – n (%)				0.11
PO	37/44 (84)	20/22 (91)	17/22 (77)	
Transition (PO + Tube)	4/44 (9)	0/22 (0)	4/22 (18)	
Tube	3/44 (7)	2/22 (9)	1/22 (5)	
CCABSID-III				
Cognitive Score <80 – n (%)	9/44 (21)	5/23 (22)	4/21 (19)	1.00
Cognitive Score – #	95 [90 - 105]	100 [90 - 105]	90 [90 - 100]	0.11

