## 4.0 Study Endpoints

- Primary Outcome
  - **Clinical outcome of feeding success for those infants transitioning to oral feeds at inception.**
    - The primary endpoint is the feeding success defined as achieving full oral feeds (defined as no need for tube feeds to maintain hydration and nutrition) and/or a  $>/=$  6-point decrease from baseline I-GERQ-R. The time frame is up to 5 weeks after enrollment.
  - **Clinical outcome of feeding success for those infants on full oral feeds at inception.**
    - The primary endpoint is the feeding success defined as maintaining full oral feeds and a  $>/=$  6-point decrease from baseline I-GERQ-R. The time frame is up to 5 weeks after enrollment.
- Secondary Outcomes
  - Clinical Outcomes
    - Length of hospital stay
    - Growth outcomes during the study period and up to 1 year
    - Independent feeding skills over time up to 1 year
    - Respiratory support during the study period and at discharge
    - Developmental outcomes with Bayley's scores at 2 years
    - Individual differences in I-GERQ-R questionnaire
  - Motility Outcomes
    - Mechanisms of aerodigestive clearance and esophageal provocation are evaluated based on esophageal motility studies at inception and after 5 weeks.
  - pH Impedance outcomes
    - 24-hour pH impedance results at inception of study and then 5 weeks later after treatment completed

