- Overall Study Endpoints: Primary clinical outcome occurs at time 2 study or at discharge if time 2 study not completed. Secondary study outcomes occur at time 2 studies. Secondary clinical outcome measures (growth characteristics, development and long term feeding outcomes) will be collected up to 24 months.
- Methods to overcome potential confounders: Data will be collected from EPIC documentation, feeding diaries, parent interviews and follow up appointments. While inpatient, these are documented regularly. After discharge, we will be dependent on parents to provide the data.
- Removal and management of subject(s) from protocol: The investigator and/or the parent(s) have the right to withdraw from study at any time and opt for the standard of care. Parent(s) that withdraw their infants from the study therapy will be encouraged to continue to remain in the study for all follow up evaluations. Those who choose completely withdrawal from the study will be encouraged to follow the standard of care; wherein, response failures are followed for secondary outcomes until 18 months.
- Secondary Outcome Measures: (up to 24 months, for Bayleys developmental score) Secondary outcome measures (growth characteristics, development and long term feeding outcomes) will be collected up to 12 months.

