## **17.0 Provisions to Monitor the Data to Ensure the Safety of Subjects\***

- Subjects are monitored throughout study procedures by a trained Registered nurse
- Meetings of the Data Safety Monitoring Board will take place on a quarterly basis.
- The study is overseen by the IRB at NCH and annual reports will be submitted
- A Data safety monitoring plan will be implemented with reports given to the DSMB and the IRB and NIDDK when appropriate.
- Subjects who remain hospitalized throughout the study period will be monitored by lab staff via review of their electronic medical record and review of bedside documentation
- Subjects who have been discharged to home will be monitored by weekly telephone communication with parents and caregivers
- Parents will be told whom to contact in case of concerns

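### The trial report and protocol section 6.1 set different times for reading the primary endpoint, and the report's rule ties it to discharge

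*Combined protocol and SAP*

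**What the plan says.** The timing of the primary endpoint is given in three places.

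- **Trial report, Outcome Measures:** the endpoint is read "at 5 weeks or sooner, whichever was earliest at discharge".
- **Protocol section 4.0:** "The time frame is up to 5 weeks after enrollment". No day is fixed.
- **Protocol section 6.1, overall study endpoints:** "Primary clinical outcome occurs at time 2 study or at discharge if time 2 study not completed". The same section and section 8.0 place the Time 2 tests at week 5, after 4 weeks of omeprazole and 1 week off it.

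The definition of success depends on feeding status at inception. Infants not yet fully oral succeed by reaching full oral feeding or by a fall of at least 6 points on the I-GERQ-R. Infants already fully oral must stay so and also show the 6-point fall.

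Discharge does not end follow-up. Section 17.0 says: "Subjects who have been discharged to home will be monitored by weekly telephone communication with parents and caregivers". Section 6.1 also lists feeding diaries, parent interviews and follow-up appointments as data sources.

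Table 2 has a row "Hospital stay Inception to Discharge – days": 23 [3-39] conventional, 27 [16-47] study, p=0.26. It reports feeding at Time 2 and feeding at discharge in separate rows. The text and tables do not give the day on which the primary endpoint was read, overall or by arm.

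**The concern.** A responder endpoint needs the same observation window for every participant. If the report's phrase means the earlier of discharge and 5 weeks, an infant who goes home on day 3 has 3 days to show a 6-point fall and one who stays has 35. Discharge follows randomisation, is plausibly driven by feeding progress, and belongs to length of stay, itself a secondary outcome. An assigned feeding strategy could therefore change when the endpoint is read as well as what is read.

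The documents' own account makes the window matter. The Discussion says I-GERQ-R scores fell over time in both arms and attributes this to maturation, so a shorter window leaves less room for a 6-point fall. For the 37 of 76 infants fully oral at inception (Table 1), success cannot occur without that fall. At least one questionnaire item looks back over a week, so on that item a reading in the first days would overlap the period before baseline.

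**Working it through.** **1. The two rules side by side.** Take the report's rule as the earlier of discharge and 5 weeks (day 35).

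| Infant | Report rule | Section 6.1 rule |
|---|---|---|
| Home on day 3, Time 2 done at week 5 | day 3 | day 35 |
| Home on day 3, Time 2 not done | day 3 | day 3 |
| In hospital to day 39, Time 2 done at week 5 | day 35 | day 35 |

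The rules disagree for every infant who is discharged early and returns for Time 2. Section 4.0 is compatible with either reading day.

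**2. The reported primary result.** 16/36 = 44.4% conventional and 13/40 = 32.5% study, a gap of 11.9 points. The uncorrected chi-square is 1.146, p=0.284, matching the stated 0.28. The p=0.26 for stay needs individual data and is taken from Table 2.

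**3. How many would be read early under the report's rule.** Both medians (23 and 27 days) are below 28, so about half or more of each arm would be read before 4 weeks. About a quarter of conventional infants left within 3 days, and about a quarter of study infants within 16.

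For closer figures, assume stay is spread evenly between the published quartiles:

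- Conventional, before day 28: 0.50 + 0.25 × (28 − 23)/(39 − 23) = 57.8%.
- Study, before day 28: 0.50 + 0.25 × (28 − 27)/(47 − 27) = 51.3%.
- Conventional, before day 35: 0.50 + 0.25 × (35 − 23)/16 = 68.8%.
- Study, before day 35: 0.50 + 0.25 × (35 − 27)/20 = 60.0%.

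Section 5.0 gives 5 weeks for the feeding strategy, where section 6.1 gives 4. These need reconciling; on a 5-week course the day-35 shares apply.

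**4. Mean reading day.** With the same assumption, a minimum stay of 0 and a cap at day 35:

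- Conventional: 0.25 × 1.5 + 0.25 × 13 + 0.1875 × 29 + 0.3125 × 35 = 20.0 days.
- Study: 0.25 × 8 + 0.25 × 21.5 + 0.10 × 31 + 0.40 × 35 = 24.5 days.

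The difference is about 4.5 days. The implied SDs are 13.9 and 11.3, so with 35 and 37 infants SE = √(13.9²/35 + 11.3²/37) ≈ 3.0, z ≈ 1.5 and p ≈ 0.13. This is a numerical imbalance, not an established difference.

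**5. Whether reading time changes the classification.** In Table 2, full oral feeding at Time 2 was 27/35 conventional and 24/37 study; at discharge it was 29/35 and 25/37. The net change is 2 infants and 1 infant. Some discharges came after week 5, so these rows show that timing matters, not what an earlier-of rule would have produced.

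**6. Direction.** A short window gives less time for the symptom score to fall, which lowers success among those discharged early. But an infant not fully oral at inception who is discharged because full oral feeding was reached counts as a success at discharge. Half of each arm or slightly more was not fully oral at inception (18/36 and 21/40, Table 1). The two mechanisms oppose each other, and the documents give no figures to weigh them.

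**The case against.** The strongest reply is that the protocol governs and is clear. Section 6.1 fixes Time 2, which is week 5, and uses discharge only as a fallback. The up-to-5-weeks frame in section 4.0 fits that rule and is not a third one. The report's phrase is awkwardly worded and can be read in more than one way. Follow-up after discharge was planned, and the Discussion refers to compliance information on infants who had gone home. On this view there is only a wording conflict.

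Much of that stands. The firm conflict is between the report and section 6.1, and nothing shows that the earlier-of rule was the one applied. It does not remove the point: the report presents its rule as set in advance, section 6.1 still permits a discharge reading whenever the Time 2 study was missed, and no count of such readings is given.

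A reader might infer that the arms were observed for different lengths of time. The documents do not support this. The medians differ by 4 days, the interquartile ranges overlap, p=0.26, and total stay has p=0.89.

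A reader might also put a figure on the bias. For example, suppose 25% of conventional and 0-10% of study infants were read early, with success of 5-15% instead of 33%. The conventional shortfall is 25% × (33 − 15) = 4.5 to 25% × (33 − 5) = 7 points. The net bias toward the bundle is then between 4.5 − 10% × 18 = 2.7 and 7 points. The 5-15% has no source in the documents, 33% is not the conventional arm's reported rate (44%), and the calculation ignores infants discharged because they already fed orally. Even if accepted, it would widen the gap in favour of conventional care and so reinforce non-superiority.

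**Conclusion.** The point holds as a conflict of timing rules. The report's rule lets a post-randomisation event set the observation window, while section 6.1 fixes week 5 with a discharge fallback. If the report's rule was applied, about half or more of each arm was read before 4 weeks: roughly 58% conventional and 51% study, assuming even spread between the Table 2 quartiles. The difference between arms is numerical only, mainly in the lower quartile (3 versus 16 days).

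The size and direction of any bias in the 33% versus 44% comparison cannot be determined, because the actual assessment day is not reported. The documents do not show that the conclusion of non-superiority is wrong. The matter should be corrected because it concerns the definition of the primary endpoint and the remedy is cheap.

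**What to change.** State one rule in the report's Outcome Measures section and in protocol sections 4.0 and 6.1: the primary endpoint is read at week 5 (Time 2), counted from randomisation, for every infant, whether in hospital or at home. For discharged infants, collect feeding status and the I-GERQ-R at the follow-up contact already planned. Make the week-5 reading independent of whether the manometry and pH-impedance tests are completed. Use the discharge value only when week 5 is missing.

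Report by arm the distribution of the actual assessment day and the number of infants scored on the discharge fallback. Add a sensitivity analysis restricted to week-5 readings. That analysis selects on a post-randomisation event, so it supplements the intention-to-treat result and does not replace it.

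The cost is a wording change, one questionnaire at an existing contact, and one short table. The small downside is that some week-5 scores would come by telephone. The weekly call sits under safety monitoring and the documents do not describe giving the I-GERQ-R that way, so it is a modest added procedure and the mode of collection should be recorded. For the completed trial, assessment day and fallback use can be reported as far as dates were recorded; week-5 scores never collected cannot be recovered.
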